## 10. MEASUREMENTS

### For clinicaltrials.gov and Stanford Clinical Trials Directory compliance

Primary Outcome Measure Definition: Proportion of patients who achieve a clinical complete response following therapy, expressed as a number and proportion without dispersion.

- Title: clinical complete response
- Time Frame: 8 (+/- 4) weeks after completion of RT and chemotherapy
- Safety Issue: Is this outcome measure assessing a safety issue? No

### 10.1 Primary Outcome Measure

The primary outcome will be assessed 8 (+/- 4) weeks following completion of RT and chemotherapy. A cCR requires multidisciplinary review and is defined as follows: 1) No residual tumor or suspicious lymph nodes on MRI (Table 1, 2), 2) no residual tumor on direct visualization with endoscopy OR a negative biopsy of any residual or suspicious ulcer or mucosal abnormality and 3) no palpable tumor on DRE (if applicable).

Table 1. Magnetic resonance imaging tumor regression grade (mrTRG)

mrTRG 1	Complete radiological response (linear scar only)
mrTRG 2	Good response (dense fibrosis, no obvious tumor signal)
mrTRG 3	Moderate response (>50% fibrosis and visible intermediate signal)
mrTRG 4	Slight response (mostly tumor)
mrTRG 5	No response/regrowth of tumor

Table 2. Malignant Morphologic Criteria and Lymph Node Size

– indicates not suspicious for malignancy; + indicates suspicious for malignancy

Number of malignant morphologic criteria*	Lymph Node Size**		
	<5mm	5-9 mm	>9 mm
None	-	-	+
Two	-	+	+
Three	+	+	+

\*Irregular borders, heterogenous signal intensity, round shape

\*\*Measured in largest short axis.

### 10.2 Secondary Outcome Measures

- Toxicity at least possibly attributed to treatment, graded using CTCAE v5 criteria and assessed up to 3 months after completion of RT and chemotherapy, expressed as a number and proportion without dispersion.
- 2-year local regrowth rate where local regrowth is defined as the presence of adenocarcinoma within the rectal wall or within the mesorectum confirmed by pathology, expressed as a percentage with its 95% confidence interval.
- DFS defined as the time from the start date of RT to the date of the first documented progression or death due to any cause assessed up to 2 years after completion of chemotherapy. Patients will be censored at the last date of follow-up if lost to follow-up prior to two years, expressed as a median with interquartile range.
- Colostomy-free survival defined as the time from the start date of RT to the date of colostomy or death due to any cause assessed up to 2 years after completion of

chemotherapy, expressed as a median with interquartile range. Patients will be censored at the last date of follow-up if lost to follow-up prior to two years.

- OS defined as death from any cause from start date of RT until death, study completion, or loss to follow-up, whichever occurs first. This will be reported as median survival time with interquartile range.

### 10.3 Exploratory Outcome Measures

- HRQOL in Appendices (B-H) will be collected by paper or electronically by the research coordinator at every study assessment visit or via mail or the myHealth messaging system (see Study Calendar). Data will be collected and stored in RedCap. Patients will receive 5 surveys (tailored to patient gender and the presence of a stoma). The entire functional assessment can be completed in less than 30 minutes, with an average of 15-20 minutes per patient.
  - Bowel function index (BFI)
    - We will use the 19-item BFI to assess bowel function. The psychometric properties of the instrument have been previously published and all subscales and total score show good internal consistency.
  - Low Anterior Resection Score (LARS)
    - All patients without a stoma will also complete 5 additional questions from the LARS. This is a validated 5 question index that was specifically developed to categorize bowel dysfunction after low anterior resection. In the LARS Score patients are asked to describe symptoms which best describe daily life. There is no specific time period, but at most the averages are over the past week. The LARS score has a range of 0-42 with 0-20 being No LARS, 21-29 being Minor LARS, and 30-42 being Major LARS.
  - Stoma QOL
    - We will also use the 21-item Stoma QOL for patients undergoing APR.
  - Sexual function
    - To assess sexual function, we will use gender-specific questionnaires: 5-item International Index of Erectile Function (IIEF-5) and 6-item Female Sexual Functioning Index.
  - Bladder function
    - Bladder function will be assessed using the International Prostate Symptom Score.
  - EuroQOL Group five dimensions Health Questionnaire (EQ-5D)
    - The EQ-5D is a widely used descriptive system of HRQOL states. It consists of five dimensions (mobility, self-care, usual activities, pain/discomfort, anxiety/depression) each of which can take one of five responses. The responses record five levels of severity (no problems/ slight problems/ moderate problems/ severe problems/ extreme problems or unable to function) within a particular EQ5D dimension. The EQ5D is almost always combined with a simple linear analogue

scale that asks respondents to rate their overall health on a vertical scale of 0 to 100.

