### **12.5.2 Analysis Plan**

For the toxicity outcome, we will calculate the proportion of patients meeting our definition of toxicity. In addition, we will present the frequency and percent of other adverse events reported in the study.

Local regrowth rate will be calculated as the proportion of patients with local regrowth based on the secondary analysis population. The local regrowth rate and its 95% confidence interval will be calculated.

Disease-free survival is defined as the time from start of RT therapy to date of progression or death due to any cause. If a subject is not known to have progressed or died, then DFS will be censored at the latest date the subject was known to be alive or disease-free (on or before the cut-off date). The DFS distribution will be estimated using the Kaplan-Meier method, and the Kaplan-Meier curves, medians and 95% confidence intervals of the medians will be presented.

Colostomy-free survival distribution will be estimated using the Kaplan-Meier method, and the Kaplan-Meier curves, medians and 95% confidence intervals of the medians will be presented.

OS is defined as the time from start of RT therapy to date of death due to any cause. If a subject is not known to have died, then OS will be censored at the latest date the subject was known to be alive (on or before the study end date). The OS distribution will be estimated using the Kaplan-Meier method, and the Kaplan-Meier curves, medians and 95% confidence intervals of the medians will be presented.

For the HRQOL measures, we will calculate the mean and standard deviations of each of the individual indices at baseline and every 3 months during the duration of the study; we will graphically depict scores at each time point. In addition, we will calculate the difference of the QoL scores at the baseline, time of cCR, and last follow up date and report summary statistics.

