MSKCC Published Bowel Function Instrument	Coding Scheme	Subscale
1. Over the last 4 weeks, how many bowel movements do you generally have in 24 hours?	If < 2 score = 5 If $\geq 2$ and $< 3$ score = 4 If $\geq 3$ and $< 4$ score = 3 If $\geq 4$ and $< 5.5$ score = 2 If $\geq 5.5$ score = 1 Must reverse for scoring < 2 bm = 1 2 bm = 2 3 bm = 3 4 - 5.5 = 4 <math>\geq 5.5 = 5</math>	Frequency
2. Do certain solid foods increase the number of bowel movements in a day?	1=Always 5=Never	Diet
3. Do certain liquids that you drink increase the number of bowel movements in a day?	1=Always 5=Never	Diet
4. Do you feel like you have totally emptied your bowels after a bowel movement?	1=Never 5=Always	Separate
5. Do you get to the toilet on time?	1=Never 5=Always	Frequency
6. Do you have another bowel movement within 15 minutes of your last bowel movement?	1=Always 5=Never	Separate
7. Do you know the difference between having to pass gas (air) and needing to have a bowel movement?	1=Never 5=Always	Separate
8. Have you used medicines to decrease the number of bowel movements (drugs like Imodium®, Lomotil®)?	1=Always 5=Never	Frequency
9. Have you had diarrhea (no form, watery stool)?	1=Always 5=Never	Frequency
10. Have you had loose stool (slight form, but mushy)?	1=Always 5=Never	Frequency
11. Have you been able to wait 15 minutes to get to the toilet when you feel like you are going to have a bowel movement?	1=Never 5=Always	Frequency
12. Have you been able to control the passage of gas (air)?	1=Never 5=Always	Separate
13. Have you limited the types of solid food you eat to control your bowel movements?	1=Always 5=Never	Diet
14. Have you limited the types of liquids you drink to control your bowel movements?	1=Always 5=Never	Diet
15. Have you had soilage (leakage of stool) of your undergarments during the day?	1=Always 5=Never	Urgency/soilage
16. Have you used a tissue, napkin, and/or pad in your undergarments during the day in case of stool leakage?	1=Always 5=Never	Urgency/soilage
17. Have you had soilage (leakage of stool) of your	1=Always 5=Never	Urgency/Soilage

undergarments when you go to bed?		lage
18. How often have you had to alter your activities because of your bowel function?	1=Always 5=Never	Urgency/Soilage
19. Compared to 4 weeks ago, how would you rate your bowel function now?	1=Always 5=Never	Separate

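### Section 10.3 assigns LARS by stoma status but Stoma QOL by operation (APR), so a patient with a stoma and no APR gets neither form, and the plan does not say how the bowel instrument is scored when a stoma is present

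*Combined protocol and SAP*

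**What the plan says.** Section 10.3 opens with a general rule: "Patients will receive 5 surveys (tailored to patient gender and the presence of a stoma". The instrument bullets then set out who gets what.

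- Bowel function: "We will use the 19-item BFI to assess bowel function". No stoma condition is attached.
- LARS: "All patients without a stoma will also complete 5 additional questions from the LARS".
- Stoma QOL: "We will also use the 21-item Stoma QOL for patients undergoing APR".
- Sexual function: "To assess sexual function, we will use gender-specific questionnaires", so one form per patient.
- Bladder: "Bladder function will be assessed using the International Prostate Symptom Score".
- EQ-5D: no restriction.

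For the analysis, section 12.5.2 states that "we will calculate the mean and standard deviations of each of the individual indices" at baseline and at intervals, and adds differences between baseline, the time of cCR and last follow-up. It gives no rule for forms or items that do not apply because of a stoma. Footnote f of the Study Calendar keeps patients on the quality-of-life forms after TME.

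**The concern.** The general rule and the LARS bullet use a state that can change from visit to visit (stoma or no stoma). The Stoma QOL bullet uses one operation. The two keys agree for a patient who never has a stoma and for an APR patient with a stoma. They disagree for a patient who has a stoma for any other reason.

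The documents make that patient foreseeable. Section 2.2.2 mentions diverting loop ileostomy and its takedown, section 2.1 distinguishes sphincter-sparing surgery from APR, and the forms continue after TME. The Stoma QOL questionnaire in Appendix D is addressed to people with ostomies in general.

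The BFI raises a separate problem. The title of its source (reference 65) confines it to bowel function after sphincter-preserving surgery. Several items, such as "Do you get to the toilet on time", make sense only with anal evacuation. If patients with a stoma complete it without a scoring rule, inapplicable answers are averaged with applicable ones.

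Longitudinal functional outcome is an objective in section 1.2. A form not given at a visit cannot be recovered later.

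**Working it through.** **Step 1. Count the forms under the written bullets.** Every patient gets one sexual-function form, the prostate symptom score and EQ-5D (3 forms). Add BFI (no restriction), LARS if there is no stoma, and Stoma QOL if APR.

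| Patient at the visit | Forms | Total | Matches the stated 5? |
|---|---|---|---|
| No stoma, no APR | 3 + BFI + LARS | 5 | yes |
| Stoma, APR | 3 + BFI + Stoma QOL | 5 | yes |
| Stoma, no APR | 3 + BFI | 4 | no |
| APR planned, no stoma yet | 3 + BFI + LARS + Stoma QOL | 6 | no, if *undergoing* covers planned APR |

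The plan's figure of five is reproduced for the first two groups only.

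**Step 2. Does a patient with a stoma get the BFI?** The text never says so outright. Three things point that way: the BFI bullet has no restriction, the LARS bullet describes its questions as additional, and the count requires it. Without the BFI, an APR patient with a stoma would have 3 + Stoma QOL = 4 forms. With it, the total is the stated 5.

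**Step 3. Which BFI items presuppose anal evacuation?** On my reading of Appendix B these are items 5, 7, 11, 12, 15, 16 and 17, which is 7 of 19.

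| Group in Appendix B | Items | Presuppose anal evacuation |
|---|---|---|
| Frequency | 1, 5, 8, 9, 10, 11 | 2 of 6 |
| Diet | 2, 3, 13, 14 | 0 of 4 |
| Urgency/soilage | 15, 16, 17, 18 | 3 of 4 |
| Separate | 4, 6, 7, 12, 19 | 2 of 5 |

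**Step 4. What can this do to a score?** Appendix B codes items 15 to 17 from 1 (*Always*) to 5 (*Never*), with high meaning good function. Suppose a patient with a stoma answers *Never* to all three because stool does not pass that way. That gives 3 × 5 = 15 points. Appendix B does not state how items are combined, so assume a simple sum. With item 18 anywhere from 1 to 5, the subscale is 16 to 20 on a range of 4 to 20. The score shows near-perfect continence whatever the patient's actual state. For items 5 and 11 the coding is reversed, so the direction of any distortion in the frequency subscale is unclear.

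**Step 5. Is there a rule that would catch this?** Appendix D gives a missing-item rule for Stoma QOL. Appendix B gives none for the BFI, and section 12.5.2 does not condition on stoma status.

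**Step 6. Count again with Stoma QOL keyed to stoma presence.** With BFI for all, every row of the first table becomes 5. If the BFI is also withheld from patients with a stoma, they get 3 + Stoma QOL = 4, and the stated five has to change.

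**The case against.** The strongest reply is that this is a wording slip. The opening sentence of 10.3 already names stoma presence as the key, and under that key everyone gets five forms. That is probably the intent. It makes the correction easy but not unnecessary, because staff and the database build will follow the bullets.

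It can also be said that quality of life is exploratory in the synopsis and in 10.3, is summarised descriptively, and plays no part in the decision rules of sections 12.2 and 12.7 or in the sample size of 37. Patients with a stoma and no APR still complete EQ-5D, bladder and sexual-function forms. All of this stands and limits the severity.

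Four stronger readings are tempting but not supported.

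- *Patients with a stoma cannot validly answer the BFI at all.* The documents do not say this. Diet, medication, stool-consistency and activity items can still be answered. The doubt attaches chiefly to the urgency/soilage subscale and to the total.
- *Change within patients is not planned.* Section 12.5.2 does plan differences from baseline. What it lacks is a condition on stoma status.
- *The LARS curve will improve because the worst-affected patients leave it.* Under section 4.2.5, TME follows from not being a candidate for organ preservation. Regrowth confirmed by biopsy is managed per standard of care. Neither is triggered by poor bowel function. The LARS group does change over time, but the documents give no direction for the effect.
- *A third to a half of patients are affected.* Such a figure can be built: at a cCR rate of 40%, 37 − 15 = 22 have TME. If 60% of those are sphincter-sparing (13) and 30 to 80% of the 13 carry a stoma (4 to 10), adding 9 APR patients gives 13 to 19 of 37, or 35 to 51%. The 60% and the 30 to 80% are assumptions found nowhere in the documents. A single range ignores ileostomy takedown over the visits. Section 4.2.5 also lets near-complete responders continue under observation, so non-cCR is not the same as TME.

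**Conclusion.** The point holds as an inconsistency in form assignment together with a missing scoring rule. As written, a patient with a stoma and no APR receives four forms instead of five, and neither LARS nor Stoma QOL. A patient with a stoma who completes the BFI can score close to the maximum on urgency/soilage and be averaged into the section 12.5.2 means.

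This rests on a literal reading of the Stoma QOL bullet, on the inference that the BFI goes to patients with a stoma (supported by the count of five), and on my classification of the BFI items. The number of patients affected cannot be derived from the documents. The consequence is limited to descriptive quality-of-life results; the cCR and toxicity rules are not touched. Severity is minor to moderate.

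**What to change.** 1. **Section 10.3, assignment.** Give Stoma QOL to any patient who has a stoma at the visit, whatever the operation, and LARS to any patient who does not. This restores five forms for every patient.
2. **Section 10.3 or Appendix B, BFI scoring.** Set the urgency/soilage subscale and the total score to missing while a stoma is present. The alternative is to omit the BFI for those patients and change the stated number of surveys to four for them.
3. **Section 12.5.2.** Report LARS and BFI means, and the differences from baseline already planned, in patients without a stoma at the time points compared. Show the number of patients with a stoma at each time.

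The cost is a short edit to each section, a stoma-status field at each quality-of-life visit if not already recorded, and a matching change to the form schedule in the database. No new instrument and no extra visits are needed.

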## **11. REGULATORY CONSIDERATIONS**

### **11.1 Institutional Review of Protocol**

The protocol, the proposed informed consent and all forms of participant information related to the study (e.g. advertisements used to recruit participants) will be reviewed and approved by the Stanford IRB and Stanford Cancer Institute Scientific Review Committee (SRC). Any changes made to the protocol will be submitted as a modification and will be approved by the IRB prior to implementation. The Protocol Director will disseminate the protocol amendment information to all participating investigators.

### **11.2 Data and Safety Monitoring Plan**

The Stanford Cancer Institute Data and Safety Monitoring Committee (DSMC) will be the monitoring entity for this study. The DSMC will audit study-related activities to determine whether the study has been conducted in accordance with the protocol, local standard operating procedures, FDA regulations, and Good Clinical Practice (GCP). This may include review of the following types of documents participating in the study: regulatory binders, case report forms, eligibility checklists, and source documents. In addition, the DSMC will regularly review serious adverse events and protocol deviations associated with the research to ensure the protection of human subjects. Results of the DSMC audit will be communicated to the IRB and the appropriate regulatory authorities at the time of continuing review, or in an expedited fashion, as needed.

### **11.3 Data Management Plan**

The Protocol Director, or his/her designee, will prepare and maintain adequate and accurate participant case histories with observations and data pertinent to the study. Study specific Case Report Forms (CRFs) will document treatment outcomes for data analysis. Case report forms will be developed using the OnCore and RedCap database system and will be maintained by the study coordinator. CRFs will be kept in a locked office, only accessible to the research team. The Investigator will certify that the data entered are complete and accurate.

Study data will be maintained in password protected databases, computer, and/or electronic files. Only research personnel listed on this protocol will have access to this information. Only the patients unique IDN will be used. Specimens will be stored under the patient's IDN. The patient's name or other public identifiers will not be included in any information shared with other investigators. Survey responses, as well as name and date of birth, will be obtained via the secure, web-based program RedCap that is PHI approved by the Stanford IRT Department. This will be password protected and only accessible by the study coordinators and PI.

## **12. STATISTICAL CONSIDERATIONS**

### **12.1 Statistical Design**

The primary objective of this study is to evaluate the efficacy of SCRT and FOLFOXIRI for rectal cancer as measured by cCR. We plan to use an optimal Simon 2 stage design to meet our primary objective. In addition, we plan to assess toxicity at the first stage.

### **12.2 Interim analyses**

We plan to conduct one interim analysis for futility. We will assess efficacy and toxicity during this analysis. Following an optimal Simon 2 stage design for efficacy, we will enroll 17 patients and assess cCR. If less than or equal to 3 patients have cCR we will stop the study for futility. Otherwise, we will continue the study and enroll 20 more patients. At the end of the study, if 11 or more patients have cCR, we will deem this treatment strategy acceptable.

We assume an acceptable toxicity rate of  $\leq 25\%$  with an unacceptable toxicity rate of 40%. Thus, at the interim analysis, if 7 or more patients have toxicity (defined as non-hematologic CTCAE v5 grade 4 or higher toxicity at least possibly related to treatment), we will stop the study and consider the treatment strategy unsafe. Otherwise, we will continue the study and conclude that the treatment is acceptable if 13 or fewer patients of the 37 total patients have toxicities. Assuming that the true toxicity rate is 25%, the probability of stopping the study at the interim analysis for toxicity is 11% and for rejecting the null hypothesis is 13%. If the true toxicity rate is 40%, the probability of stopping the study early is 55% and probability of rejecting the null hypothesis is 74%.

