#### **7.2.1.1 Reporting SAEs**

- SAEs should be graded according to the NCI Common Terminology Criteria for Adverse Events, Version 5.0. NCI CTCAE v5 can be downloaded from [http://ctep.cancer.gov/protocolDevelopment/electronic\\_applications/ctc.htm](http://ctep.cancer.gov/protocolDevelopment/electronic_applications/ctc.htm)"

SAEs Grade 3 and above require prompt reporting. Routine SAE Grade 3+ reporting will be to [[contact]](mailto:[contact]). These reports will also be sent to [name] and Stanford Research Staff (Research Nurse or Research Coordinators) with subject line: "SECURE: SHORT FOX STUDY Serious Adverse Event." A Case Report Form (CRF) describing the event must be supplied and can be sent as an attachment to the email. It could be generated from the OnCore entry (as a pdf or

report).

Stanford research staff will notify Stanford IRB via ‘eProtocol’ as per regulatory and institutional guidelines. The SAE may also be forwarded to other Stanford regulatory boards, e.g., DSMC, as applicable.

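### Section 12.2 ties the 7-of-17 toxicity stop to the single interim analysis, so patients can be enrolled after the 7th event has already settled the decision

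*Combined protocol and SAP*

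**What the plan says.** Section 12.2 schedules one look before the end: "We plan to conduct one interim analysis for futility. We will assess efficacy and toxicity during this analysis". For that look, "we will enroll 17 patients and assess cCR". The toxicity limit belongs to the same occasion: "at the interim analysis, if 7 or more patients have toxicity", the study stops and the strategy is considered unsafe. A qualifying event is "defined as non-hematologic CTCAE v5 grade 4 or higher toxicity at least possibly related to treatment". If neither limit is met: "Otherwise, we will continue the study and enroll 20 more patients". At the end, the investigators will "conclude that the treatment is acceptable if 13 or fewer patients of the 37 total patients have toxicities"; section 12.7 repeats this criterion. Section 12.1 likewise places the toxicity assessment at the first stage.

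Two other provisions concern safety while the trial runs. Section 7.2.1.1 says "SAEs Grade 3 and above require prompt reporting", and section 11.2 says "the DSMC will regularly review serious adverse events and protocol deviations associated with the research". Neither mentions a count of 7, a pause in accrual, or the limit in 12.2.

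**The concern.** The number of patients with a qualifying toxicity can only rise. When the 7th of the first 17 patients has one, the interim verdict is known, whatever happens to the rest. The plan nevertheless attaches the verdict to a look that waits for cCR in the 17th patient, roughly half a year after that patient starts radiotherapy. Between the deciding event and the look, nothing written prevents further patients from entering a strategy that already meets the trial's own definition of unsafe. Those patients add nothing to the toxicity decision.

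**Working it through.** **Inputs.** From 12.2: 17 patients in stage 1, 20 in stage 2, stop at 7 or more of 17, unacceptable at 14 or more of 37, reference toxicity rates of 25% and 40%. From 12.6.1: accrual of 0-1 patients a month.

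**Step 1: reproduce the plan's figures.** With X1 ~ Bin(17, p) and X2 ~ Bin(20, p):
- Interim stop = P(X1 ≥ 7).
- Total rejection = P(X1 ≥ 7) + Σ over x = 0 to 6 of P(X1 = x) · P(X2 ≥ 14 − x).
- p = 0.25: 0.1071, and 0.1071 + 0.0247 = 0.1318 (plan: 11% and 13%).
- p = 0.40: 0.5522, and 0.5522 + 0.1876 = 0.7398 (plan: 55% and 74%).

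All four agree. They describe a rule with looks at 17 and 37 only.

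**Step 2: when is the interim decision fixed?** Let T be the enrolment number of the patient with the 7th event. Then P(T = n) = C(n−1, 6) · p^7 · (1−p)^(n−7) for n = 7 to 17. These terms sum to P(X1 ≥ 7), because the rule fires exactly when T ≤ 17. Stopping at T therefore gives the same decision in every trial, and the four probabilities stand.

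At p = 0.40, P(T = 17) = 8008 · 0.4^7 · 0.6^10 = 0.0793, so P(T < 17) = 0.5522 − 0.0793 = 0.473.

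**Step 3: patients after the deciding event.** The count is 17 − T, first assuming that each event is known at once.

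| True rate | Rule fires | T before patient 17 | Mean T, given firing | Later patients, given firing | Later patients, all trials |
|---|---|---|---|---|---|
| 25% | 0.107 | 0.080 | 14.9 | 2.1 | 0.23 |
| 40% | 0.552 | 0.473 | 13.8 | 3.2 | 1.75 |
| 50% | 0.834 | 0.773 | 12.8 | 4.2 | 3.54 |

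The largest possible number is 17 − 7 = 10.

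**Step 4: reporting lag.** If an event becomes known only after L further patients have entered, the count is max(0, 17 − T − L). The documents give no lag, so L is an assumption.

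| Later patients, given firing | L = 0 | L = 2 | L = 4 | L = 6 |
|---|---|---|---|---|
| 25% rate | 2.1 | 0.8 | 0.25 | 0.05 |
| 40% rate | 3.2 | 1.6 | 0.6 | 0.2 |

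For scale: 37 patients over the 60 months to primary completion (3.4) is 37/60 = 0.62 a month. At that rate, lags of 2, 4 and 6 patients are about 3.2, 6.5 and 9.7 months from enrolment to a known event. Treatment itself takes about 1 + 2 + 16 = 19 to 1 + 4 + 18 = 23 weeks (4.2, 4.2.2.1, 4.2.2.4), and toxicity counts for up to 3 months afterwards (10.2).

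**Step 5: if accrual is not held at 17.** The cCR assessment comes 8 ± 4 weeks after chemotherapy (4.2.4), so 19 + 4 = 23 to 23 + 12 = 35 weeks after the start of radiotherapy, or about 5 to 8 months. At up to 1 patient a month, up to about 5 to 8 more patients could enter before the interim decision. A running count would spare some of them, depending on when the 7th event is confirmed.

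**The case against.** The toxicity rule is a legitimate two-look design whose stated probabilities are all right, so this is a refinement and not the repair of an error. That stands.

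A reader might infer that the plan requires enrolment to go on after the 7th event, or that seven grade 4 events would pass unnoticed. The documents support neither. Section 12.2 is silent on enrolment before the look, severe events are reported promptly, and the safety committee could act on its own judgment. What is missing is a link between its review and the number 7.

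A reader might also take 3.2 patients as the expected saving. That figure is conditional on a 40% rate, on the rule firing and on instant knowledge of events. Averaged over all trials it is 1.75, and a modest lag removes half or more of it. At illustrative true rates of 10% or 15%, the interim limit fires with probability 0.0008 or 0.008, and the saving is negligible.

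Finally, a reader might extend the argument to the 14th event overall. That goes too far. Sections 12.2 and 12.7 state a conclusion at 37 patients, not a stop. At the 14th event only the negative final conclusion is fixed. Halting accrual there would add a rule that the sponsor did not adopt and would shorten the cCR and toxicity samples.

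**Conclusion.** The point holds for the 7-of-17 limit, as an inexpensive improvement. As written, patients can be enrolled after the stop decision is already determined, and no ongoing safety provision carries a count that would prevent it. The number affected is small: at a 40% rate, 3.2 patients given firing with instant knowledge, and between 1.6 and 0.2 with an assumed lag of 2 to 6 patients. At the acceptable 25% rate, the average over all trials is 0.23. These figures assume independent events at a constant rate and accrual held at 17. The wording of 12.2 suggests such a hold, since the next 20 patients follow the decision, but does not state it. Without a hold the exposure could be larger. The plan's operating characteristics are correct and unaffected.

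**What to change.** Add to 12.2 that the 7-of-17 limit applies as soon as the 7th patient among the first 17 has a confirmed qualifying toxicity, and that accrual then stops without waiting for the interim analysis. Keep the running count from the promptly reported serious events together with the other recorded adverse events, because a grade 4 toxicity need not meet the seriousness definition in 7.2.1. Pass the count to the safety committee named in 11.2. State also whether accrual is held while the first 17 are assessed.

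The stated 11%/13% and 55%/74% need no change, nor do the limits or the sample size. The work is one sentence and a tally of data already collected. When the trial stops this way there are two costs: fewer patients for the cCR estimate, and a toxicity proportion biased somewhat upward. For example, stopping with the 7th event at patient 12 gives 7/12 = 58%, whereas 7 of 17 is 41%. The report should say that the sample was curtailed.

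Prompt notification of the committee at the 14th event overall is an optional addition, not a correction.
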